7.6.2 Additional Safety Endpoints

The following analyses for the additional safety endpoints will be conducted in the FAS and mITT analysis sets and summarized descriptively as the total number of events, number of subjects with events, and percentage of subjects with events:

- Occurrence of individual PAEs from the primary composite
- Occurrence of Serious Adverse Device Effects (SADEs)

- Occurrence of Serious Adverse Events (SAEs) within 7 days (early-onset), 8-30 days (peri-procedural), and >30 days (late onset) of initial ablation procedure, separately for each timeframe
- Occurrence of non-SAEs
- Occurrence of clinically symptomatic severe PV stenosis as documented by computed tomography (CT)/ magnetic resonance angiogram (MRA) as assessed by a central core lab

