--	---

	
28. Presenting contra-indications for the devices used in the study, as indicated in the respective Instructions For Use (IFU)
 
Additional exclusion criteria for Wave I subjects:
 
29. Contraindication for MRI such as use of contrast agents due to advanced renal disease, claustrophobia etc. (at PI discretion)
 
30. Presence of iron-containing metal fragments in the body
 
31. Unresolved pre-existing neurological deficit.
 
32. Uncontrolled significant GastroEsophageal Reflux Disease (GERD)

Safety Assessments
	
The safety endpoint is the incidence of early onset Primary Adverse Events (PAEs) (within seven (7) days of the initial ablation procedure).
 
Additional safety assessments on neurological lesions, esophageal lesions and PV stenosis will be performed for the Wave I subjects.

Statistical Analysis
	
The main phase of the study (Wave II) will use a Bayesian adaptive design to determine the sample size. The timing of sample size selection interim analyses will be described in the Statistical Analysis Plan (SAP). A maximum of 330 subjects may be enrolled in the main study phase. An additional interim analysis will be performed for claiming early trial success when 30 subjects reach full 12-month of follow-up and all subjects in three months of follow-up. If the criteria for early success are met, filing for CE Mark will be performed while 12-month follow-up is ongoing in the remaining subjects.
 
Final Primary safety analysis
 
The final analysis for the primary safety endpoint will use a beta-binomial model with a non-informative uniform prior. The endpoint will be considered a success if the posterior probability of the safety rate being less than 14% is greater than 0.975.
 $H_0: \Pr(P_s < 0.14) \leq 0.975$ $H_a: \Pr(P_s < 0.14) > 0.975$ 
Final Primary effectiveness analysis
 
The final analysis for the primary effectiveness endpoint will use a beta-binomial model with a non-informative uniform prior. The endpoint will be considered a success if the posterior probability of the primary effectiveness success rate being greater than 50% is greater than 0.9775.
 $H_0: \Pr(P_E > 0.50) \leq 0.9775$ $H_a: \Pr(P_E > 0.50) > 0.9775$

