#### 20.4.4.2 Early Success Interim Analysis for the Main Study Phase

An interim analysis will be performed for claiming early trial success in Wave II when 30 subjects in the PP-Wave II analysis set reach full 12-month of follow-up and all subjects in the mITT-Wave II analysis set reach three months of follow-up. At this interim, the trial will declare early success if both safety and effectiveness objectives are met:

1. The posterior probability of the safety rate being less than 14% is greater than 0.975
2. The posterior probability of the effectiveness proportion  $p_E$  being greater than 50% is greater than 0.9975.

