7.4 Analysis of Primary Endpoints

A single interim analysis is planned for an early success evaluation. The interim analysis will be performed when 30 subjects complete full 12 months of follow-up and all subjects complete 3 months of follow-up in the mITT analysis set. If early success is achieved, an early success interim analysis Clinical Study Report (CSR) will be compiled to present the results of the study success. If early success is not achieved, then the final primary endpoint analyses will be performed at the end of the study using the full follow-up data.

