7.6 Analysis of Additional Endpoints

No formal statistical hypothesis or inferential statistics will be formulated or performed for the additional endpoints. Descriptive statistics will be provided on all additional endpoints in the analysis sets specified below. Procedural data, additional safety endpoints, and additional effectiveness endpoints using Kaplan-Meier estimates and plots where relevant will be presented at the time of early success interim analysis with available data. All additional endpoints will be analyzed at the time of final analysis using full 12-month follow-up data.

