7.6.3 Additional Effectiveness Endpoints

The following analyses for the additional effectiveness endpoints will be conducted in the mITT and PP analysis sets unless otherwise specified and summarized descriptively:

- **Ablation by non-study catheter for PV isolation:** The number and percentage of subjects and number and percent of clinically relevant targeted PVs ablated by a non-study catheter (NSC) for PVI will be summarized.

- Rate of ablation by NSC for PVI among all clinically relevant targeted pulmonary veins:

$$= \frac{\text{Number of PVs ablated by NSC}}{\text{Number of ablated PVs}}$$

- Rate of ablation by NSC for PVI among subjects:

$$= \frac{\text{Number of subjects with at least one PV ablated by NSC}}{\text{Total number of subjects ablated for PVI}}$$

- **Acute PV reconnection:** The number and percentage of subjects and number and percentage of targeted PVs where acute reconnection was identified by adenosine/isoproterenol challenge.

- Rate of acute PV reconnection among targeted veins:

$$= \frac{\text{Number of PVs with reconnection after adenosine/isoproterenol challenge}}{\text{Total number of PVs undergoing adenosine/isoproterenol challenge}}$$

- Rate of acute PV reconnection among subjects:

$$= \frac{\text{Number of subjects with PV reconnection in at least one PV after adenosine/isoproterenol challenge}}{\text{Total number of subjects undergoing adenosine/isoproterenol challenge in all targeted PVs}}$$

- **Repeat ablation during the 12-month follow-up period**

- **Occurrence of repeat procedures:** Kaplan-Meier estimates and plots will be used to characterize the time to the first repeat ablation procedure for study related arrhythmia. The probability of freedom from repeat ablation for study related arrhythmia at each follow-up timepoint post index procedure will be presented. Additionally, the total number of repeat procedures, number of subjects undergoing a repeat procedure, and percentage of subjects undergoing a repeat procedure will be presented by type of arrhythmia treated (overall (all

arrhythmias), AF and AFL or AT (left atrium)), and by timing of the repeat procedure (during the blanking period (Day 1-90) and during the evaluation period (Day 91-365)).

- **PV reconnection:** The number and percentage of subjects and number and percentage of targeted PVs at the repeat procedure where PV reconnection was observed

- Rate of PV reconnection among previously isolated veins:

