10.3 Adaptive Sample Size Determination

Sample size selection interim analyses will be performed when 180 and 255 subjects (excluding roll-in) are enrolled in the mITT analysis set. Predictive probability of success for the effectiveness endpoint will be used to determine whether the sample size at each interim analysis will be sufficient or if the trial enrollment will continue. Sample size simulations were performed using performance goals of 14% and 50% respectively for the safety and effectiveness endpoints.

At the time of each interim analysis, predictive probability of success for the effectiveness will be calculated once using the current sample size and another time using the maximum sample size allowed. If the effectiveness predictive probability is greater than 90%, or if the effectiveness predictive probability with the maximum sample size of 330 is less than 2.5%, then the enrollment will be stopped. Otherwise the enrollment will continue.

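### At the early-success look, late-onset SAEs (>30 days) are reported as a raw percentage of subjects when only about 57–76% of Day 31–365 follow-up has accrued, which understates the 12-month late-SAE risk

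*SAP*

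**What the plan says.** SAP Wave II 7.6.2 covers SAEs in three windows: "Occurrence of Serious Adverse Events (SAEs) within 7 days (early-onset), 8-30 days (peri-procedural), and >30 days (late onset) of initial ablation procedure". In the FAS and mITT sets they are "summarized descriptively as the total number of events, number of subjects with events, and percentage of subjects with events". No number at risk, patient-time or censoring is specified. Section 7.1 bases percentages on subjects without missing data and does not say how to treat a window that is still open.

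Section 7.6 states that procedural data and the additional safety and effectiveness endpoints "will be presented at the time of early success interim analysis with available data", and that all are analysed again on full 12-month data at the final analysis. It mentions Kaplan-Meier where relevant, in the phrase about effectiveness endpoints. Section 7.6.2 names no Kaplan-Meier estimate.

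The trigger in SAP Wave II 7.4 is: "The interim analysis will be performed when 30 subjects complete full 12 months of follow-up and all subjects complete 3 months of follow-up", counted in the mITT set. Protocol 20.4.4.2 counts the completers differently: "when 30 subjects in the PP-Wave II analysis set reach full 12-month of follow-up". If early success is met, the Protocol Summary (Statistical Analysis) says that "filing for CE Mark will be performed while 12-month follow-up is ongoing in the remaining subjects".

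For repeat ablation, SAP Wave II 7.6.3 plans Kaplan-Meier for time to first repeat procedure for study-related arrhythmia. It then adds counts and percentages "by timing of the repeat procedure (during the blanking period (Day 1-90) and during the evaluation period (Day 91-365".

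**The concern.** A raw percentage estimates the risk over a window only if each subject in the denominator has been observed through that window. At the early-success look this holds for 0–7 and 8–30 days, apart from early drop-outs. It does not hold for >30 days, where most subjects still have follow-up to come. The three percentages stand in one table, and nothing tells the reader that the third rests on partial observation.

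The bias has one direction: the late figure comes out too low. It also falls in the report most likely to be filed. In SAP Appendix I Table 3.a (7% safety rate, 65% effectiveness rate), early success is declared in 0.8316 of simulated trials. The primary safety endpoint covers 7 days apart from three event types counted later, so the >30-day SAE row is one of the main views of later safety.

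The SAP handles the same problem elsewhere at this look. Event-free subjects are censored in the effectiveness model (7.4.3), symptomatic recurrence is shown by Kaplan-Meier (7.5), and site-level effectiveness is withheld because follow-up is ongoing (7.4.6).

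**Working it through.** **Inputs.** Monthly enrolment comes from SAP Appendix I Table 1 (realistic, slow, fast). Possible sample sizes come from Appendix I 10.3 ("Sample size selection interim analyses will be performed when 180 and 255 subjects (excluding roll-in) are enrolled in the mITT analysis set") and the maximum of 330. The trigger is that of SAP 7.4. The late window is taken as Day 31–365, that is 335 days.

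**Check against a stated figure.** The documents give no accrued fraction for the early-success look. The nearest figure is in SAP Section 6: at N = 180 under realistic enrolment, about 30%, 18% and 2% of subjects have 3–6, 6–9 and 9–12 months. Interpolating cumulative enrolment linearly within months gives 30.0%, 17.2% and 3.3%, which agrees within 2 points. The mix stated for N = 255 (27%, 27%, 19%) does not reproduce under the realistic schedule, which gives about 34%, 18% and 12%. The slow schedule is closer, at about 28%, 26% and 11%.

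**Formulas.**
- Look time T = max(entry of 30th subject + 12 months, entry of last subject + 3 months).
- Follow-up f = min(T − entry, 365 days).
- Late share accrued = mean of min(max(f − 30, 0), 335) / 335.
- For Day 91–365, the same with 90 and 275 days.

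**Worked case (realistic, N = 255).** Cumulative enrolment is 18 at month 2 and 31.5 at month 3, so the 30th subject enters at 2 + 12/13.5 = 2.89, and 12 months later is 14.89. Cumulative enrolment is 246 at month 12, so the 255th enters at 12 + 9/30 = 12.30, and 3 months later is 15.30. The look is at month 15.30. Subjects with 12 months entered by month 3.30: 31.5 + 0.30 × 7.5 = 33.75, so 33 of 255, or 12.9%. Mean late follow-up is 197.8 days, and 197.8/335 = 59.0%.

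**All cases, no drop-out.** The last column assumes a true late-SAE risk of 10% with constant hazard λ = −ln(0.9)/335, and averages 1 − exp(−λ × late days) over subjects.

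| Accrual | N | Look (month) | With 12 months | Day 31–365 accrued | Day 91–365 accrued | Raw % if truth is 10% |
|---|---|---|---|---|---|---|
| Realistic | 180 | 14.9 | 16.7% | 68.3% | 61.4% | 6.92 |
| Realistic | 255 | 15.3 | 12.9% | 59.0% | 50.1% | 6.00 |
| Realistic | 330 | 18.0 | 21.8% | 67.9% | 60.9% | 6.87 |
| Slow | 180 | 15.9 | 16.7% | 68.2% | 61.2% | 6.91 |
| Slow | 255 | 17.4 | 17.3% | 65.3% | 57.8% | 6.62 |
| Slow | 330 | 21.0 | 38.2% | 75.9% | 70.7% | 7.65 |
| Fast | 180 | 15.4 | 16.7% | 68.2% | 61.3% | 6.92 |
| Fast | 255 | 15.4 | 11.8% | 56.5% | 47.0% | 5.75 |
| Fast | 330 | 17.9 | 18.5% | 65.0% | 57.3% | 6.58 |

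Weighting the realistic rows by the sample-size probabilities in Table 3.a at 65% effectiveness gives 0.5535 × 68.3 + 0.2854 × 59.0 + 0.1611 × 67.9 = 65.6% of late follow-up accrued.

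**Sensitivity to drop-out.** A simulation with Poisson accrual and 5% yearly drop-out gives 58–73% for Day 31–365. If about 36 subjects must be enrolled to obtain 30 completers, the minimum rises to 61%.

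**Sensitivity to hazard shape.** Let cumulative hazard grow as −ln(0.9) × √(t/335), so that half falls in the first quarter of the window. A true 10% then shows as 7.4–8.6%. Other shapes with about half of the events in that quarter give values between roughly 7.1% and 9.0%.

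**The case against.** The strongest reply is that nothing formal rests on this row. The additional endpoints are descriptive, early success is decided on the primary endpoints, and everything is re-analysed on 12-month data. Device- or procedure-related death, PV stenosis and atrio-esophageal fistula count as primary adverse events even after 7 days. Counts stand beside the percentages, the tables are described as using available data, and a DMC reviews safety. All of this is correct and limits the point to how one row is presented in one report. It does not make the percentage an estimate of the 12-month risk.

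A second reply is that windows of 7, 23 and about 335 days are never comparable as raw percentages. That is also true, but incomplete observation lowers the late figure further, and only at this look.

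Some stronger readings are tempting, and the documents do not support them:
- **That repeat ablation after blanking is reported only as a raw percentage.** SAP 7.6.3 plans Kaplan-Meier with freedom from repeat ablation at each follow-up timepoint, and 7.6 calls for it at this look. Among those repeat-free at 3 months, the first-repeat risk over Day 91–365 follows as 1 − S(12)/S(3).
- **That low repeat-ablation figures hide harm.** Repeat ablation is listed under effectiveness, and Protocol 15.1.1 does not treat re-ablation for AF or pre-existing AFL/AT as an adverse event.
- **That less than half of late safety follow-up may have accrued.** The 47% minimum belongs to Day 91–365 only. For late SAEs the minimum is 57%.
- **That the share of follow-up equals the share of events seen.** This depends on the hazard shape, and the documents give none for SAEs.
- **That drop-out must make matters worse.** The trigger waits for 30 completers, so drop-out can also delay the look.

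**Conclusion.** The point holds for late-onset SAEs in the early-success report. With 57–76% of Day 31–365 follow-up accrued (59–68% under realistic accrual) and 12–38% of subjects at 12 months, the raw percentage falls below the 12-month risk if any late hazard remains. Only the direction is firm. For an assumed true 10% risk, the size is about 5.8–7.7% shown under constant hazard, with less understatement under front-loading.

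This rests on three assumptions: the Table 1 schedules, the SAP trigger, and a denominator of the whole FAS or mITT set, which is the natural reading of 7.6.2. The mismatch in the stated N = 255 mix does not change the conclusion, because the slow schedule that fits it better gives 65%. Counting the 30 completers in the PP set, as the protocol does, could only delay the look.

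For repeat ablation the issue is secondary. No hypothesis test, error rate or stopping rule is affected, and the final 12-month report is sound on this point. It is a worthwhile, inexpensive improvement to a report that may be filed.

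**What to change.** In SAP Wave II 7.6.2, for the early-success report only, present >30-day SAEs in two further ways beside the counts:

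1. A Kaplan-Meier cumulative incidence of first late SAE through Day 365, censored at last contact, with numbers at risk.
2. Events per 100 patient-years of follow-up after Day 30.

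In 7.6.3, mark the Day 91–365 repeat-ablation percentage in that report as incompletely observed and refer to the Kaplan-Meier estimate already planned. Leave the 0–7 day, 8–30 day and Day 1–90 figures and the final report as they are.

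The cost is a few lines of programming on data already collected. The early late-SAE figure becomes less favourable. The Day-365 estimate will have wide intervals, because only 12–38% of subjects will have been followed that far, and the numbers at risk will make this visible.

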7.6.3 Additional Effectiveness Endpoints

The following analyses for the additional effectiveness endpoints will be conducted in the mITT and PP analysis sets unless otherwise specified and summarized descriptively:

- **Ablation by non-study catheter for PV isolation:** The number and percentage of subjects and number and percent of clinically relevant targeted PVs ablated by a non-study catheter (NSC) for PVI will be summarized.

- Rate of ablation by NSC for PVI among all clinically relevant targeted pulmonary veins:

$$= \frac{\text{Number of PVs ablated by NSC}}{\text{Number of ablated PVs}}$$

- Rate of ablation by NSC for PVI among subjects:

$$= \frac{\text{Number of subjects with at least one PV ablated by NSC}}{\text{Total number of subjects ablated for PVI}}$$

- **Acute PV reconnection:** The number and percentage of subjects and number and percentage of targeted PVs where acute reconnection was identified by adenosine/isoproterenol challenge.

- Rate of acute PV reconnection among targeted veins:

$$= \frac{\text{Number of PVs with reconnection after adenosine/isoproterenol challenge}}{\text{Total number of PVs undergoing adenosine/isoproterenol challenge}}$$

- Rate of acute PV reconnection among subjects:

$$= \frac{\text{Number of subjects with PV reconnection in at least one PV after adenosine/isoproterenol challenge}}{\text{Total number of subjects undergoing adenosine/isoproterenol challenge in all targeted PVs}}$$

- **Repeat ablation during the 12-month follow-up period**

- **Occurrence of repeat procedures:** Kaplan-Meier estimates and plots will be used to characterize the time to the first repeat ablation procedure for study related arrhythmia. The probability of freedom from repeat ablation for study related arrhythmia at each follow-up timepoint post index procedure will be presented. Additionally, the total number of repeat procedures, number of subjects undergoing a repeat procedure, and percentage of subjects undergoing a repeat procedure will be presented by type of arrhythmia treated (overall (all

arrhythmias), AF and AFL or AT (left atrium)), and by timing of the repeat procedure (during the blanking period (Day 1-90) and during the evaluation period (Day 91-365)).

- **PV reconnection:** The number and percentage of subjects and number and percentage of targeted PVs at the repeat procedure where PV reconnection was observed

- Rate of PV reconnection among previously isolated veins:

$$= \frac{\text{Number of previously isolated PVs with reconnection identified at repeat}}{\text{Total number of previously isolated veins in subjects undergoing repeat ablation}}$$

- Rate of PV reconnection among subjects:

$$= \frac{\text{Number of subjects with PV reconnection identified at repeat in at least 1 previously isolated vein}}{\text{Total number of subjects undergoing repeat ablation with PVI in all targeted veins at index}}$$

- **Freedom from documented (symptomatic and asymptomatic) atrial fibrillation (AF):** Kaplan-Meier estimates and plots will be used to characterize the time to first documented (symptomatic and asymptomatic) AF recurrence based on electrocardiographic data (≥ 30 seconds on arrhythmia monitoring device) during the effectiveness evaluation period (Day 91-Day 365). Acute procedural failure (i.e., failure to confirm entrance block in all PVs except those that are silent and/or cannot be cannulated post-procedure, use of non-study catheter for PV isolation, and failure to have PFA delivery with the study catheter due to IRE system malfunctions) will also be considered a failure. Subjects without effectiveness failure who undergo a repeat ablation procedure during the blanking period where PVs were ablated with a commercially available catheter and generator will be considered non-assessable for long-term effectiveness of the IRE ablation system and thus will be excluded from this analysis.

The probability of freedom from documented (symptomatic and asymptomatic) AF at each follow-up timepoint post blanking will be presented. The event-free rate will also be summarized descriptively as the number and percent of subjects free from documented AF during the evaluation period.

- **Freedom from documented (symptomatic and asymptomatic) atrial arrhythmia (AF, AT or AFL) with additional failure modes:** Kaplan-Meier estimates and plots will be used to characterize the time to first documented (symptomatic and asymptomatic) AF, AT or AFL recurrence based on electrocardiographic data (≥ 30 seconds on arrhythmia monitoring device) during the effectiveness evaluation period (Day 91-Day 365). Subjects without effectiveness failure who undergo a repeat ablation procedure during the blanking period where PVs were ablated with a commercially available catheter and generator will be considered non-assessable for long-term effectiveness of the IRE ablation system and thus will be excluded from this analysis.

The probability of freedom from documented (symptomatic and asymptomatic) AF, AT or AFL at each follow-up timepoint post blanking will be presented. The event-free rate will also be summarized descriptively as the number and percent of subjects free from documented AF, AT, or AFL during the evaluation period. The following criteria will also be deemed failures:

- Acute procedural failure (i.e., failure to confirm entrance block in all PVs except those that are silent and/or cannot be cannulated post-procedure, use of non-study catheter for PV isolation, and failure to have PFA delivery with the study catheter due to IRE system malfunctions)
- Taking a new class I/III AAD for AF, AT or AFL or a previously failed class I/III AAD at a greater than the highest ineffective historical dose for AF, AT or AFL during the effectiveness evaluation period
- Greater than 2 repeat ablations for AF, AT or AFL in the blanking period or any repeat ablation for AF, AT or AFL during the effectiveness evaluation period

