#### 14.2.5 Repeat Ablation Procedures

Repeat procedures may be performed at the discretion of the investigator. It is highly recommended to collect arrhythmia documentation (in example documented recurrences) before performing a repeat procedure.

Repeat procedures during the blanking period (90 days post index procedure) must be conducted with the investigational device, with or without focal touch-up, if the arrhythmia is due to PV triggers. If the arrhythmia is due to non-PV triggers and the subject is treated with a commercially available ablation catheter and generator, the subject will be excluded from the long term effectiveness cohort.

Repeat procedures performed after the blanking period may be managed per investigator discretion using a commercially available ablation catheter and generator.

The follow-up schedule will remain based on the initial ablation procedure.

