5. Performed the day before procedure or day of ablation procedure to rule out the presence of atrial thrombus using one of the following modalities TEE, ICE, CT, MRI.
6. If Standard of care assessment (For pre-procedure, can be performed before ICF signature)
7. Arrhythmia monitoring via remote monitoring once per week as from 3-month follow-up visit to the end of 5-month follow-up and monthly as of 6-month follow-up visit and whenever subject feels symptoms.
8. Arrhythmia monitoring via 24H Holter, site to contact subject and verify if any symptoms experienced during the Holter monitoring.
9. Information on any repeat ablation after the index procedure will be collected
10. Concomitant medication: only cardiac (i.e. anti-arrhythmia drugs, anticoagulation regimen) & index procedure related (i.e. adenosine, pain medication)
11. AEs must be collected from the time the subject signs the informed consent onward.
12. To be completed within 6 months prior to ablation procedure, For Wave I subjects: CT-MRA to be repeated at 3M FU. For Wave I and Wave II subjects, CT-MRA to be repeated post procedure in case subject presents with PV stenosis symptoms.
13. Endoscopy preferable prior to discharge and no later than 72-hours after procedure. For procedures on Friday a window of a maximum of 96 hours is justified.
14. If observations are noted on the post-procedure MRI, the subject must have follow-up MRI at the next follow-up visit(s) until observations are resolved.
15. A certified/qualified physician expert must perform neurologic exams at pre-and post-ablation and possibly at other follow-up visits, pending previous findings of micro-emboli/neurologic deficits.
16. To be completed within 72-hours pre-procedure. For procedures on Monday a window of a maximum of 96 hours is justified.
17. To be completed within 72-hours post-procedure. For procedures on Friday a window of a maximum of 96 hours is justified.
18. Full neurological follow up to be undertaken if neurologic symptoms and/or cerebral ischemic lesions identified in a prior evaluation.
19. If subject returns for a potential study related cardiovascular or neurological visit outside of the protocol-defined visit schedule as deemed required per investigators discretion.
20. Patient questionnaires will only be used in countries with validated languages.

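### The vein-level PV reconnection rate keeps veins not assessed at the repeat procedure in its denominator, so if any are unassessed it reports the lowest value the data allow

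*SAP*

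**What the plan says.** Wave II SAP 7.6.3 defines the vein-level rate as a fraction. The numerator is the "Number of previously isolated PVs with reconnection identified at repeat" and the denominator is the "Total number of previously isolated veins in subjects undergoing repeat ablation". Wave I SAP 7.6.3 uses the same fraction.

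The lead sentence above the formula describes the measure as the "number and percentage of targeted PVs at the repeat procedure where PV reconnection was observed".

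Earlier in the same section, the acute reconnection rate among veins is divided by the "Total number of PVs undergoing adenosine/isoproterenol challenge", that is, by veins that were actually tested.

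On repeat procedures, Protocol 14.2.5 says: "Repeat procedures performed after the blanking period may be managed per investigator discretion using a commercially available ablation catheter and generator". For the blanking period it also provides for the case that starts "If the arrhythmia is due to non-PV triggers and the subject is treated with a commercially available ablation catheter and generator". It does not ask for all PVs to be re-mapped at a repeat. On data capture, a note to the protocol's schedule tables says only: "Information on any repeat ablation after the index procedure will be collected".

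**The concern.** Reconnection can be identified only in a vein that someone examines. The numerator depends on examination at the repeat and the denominator does not. A previously isolated vein that was not checked therefore adds one to the denominator and nothing to the numerator, exactly like a vein that was checked and found isolated.

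Unchecked veins are foreseeable under the plan. Repeats for non-PV triggers are provided for, and later repeats are left to the investigator. Protocol Appendix 1 names isthmus-dependent flutter and AV nodal reentry as new arrhythmias that may arise. SAP 7.6.3 summarises repeats for all arrhythmias and does not limit the reconnection denominator to PV-related ones.

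At stake is how a descriptive measure of late reconnection is read. If some veins were not assessed, the report would show the most favourable figure compatible with the data and would not say so. The mismatch between lead sentence and formula is a second problem: two programmers working from the same SAP could produce different rates.

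**Working it through.** The documents give no reconnection rate, no number of repeats and no share of veins assessed, so there is no stated figure to reproduce. The check is algebraic, followed by illustrations on assumed values.

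**Definitions**

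- V: previously isolated veins in subjects with a repeat ablation (the SAP denominator).
- u: share of V not assessed at the repeat.
- r: reconnection rate among the assessed veins.
- q: unknown reconnection rate among the unassessed veins, between 0 and 1.

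**Formulas**

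- Assessed veins: V(1−u). Reconnections identified: rV(1−u).
- Rate as written: rV(1−u)/V = r(1−u).
- Rate among assessed veins: r.
- Rate over all V: r(1−u) + qu, which runs from r(1−u) at q = 0 to r(1−u)+u at q = 1.

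The written rate is therefore the lower end of the possible range whenever u is above zero. It lies below the assessed-vein rate by ru. If u = 0, all these rates coincide.

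**Illustration (r and u are assumptions, not from the documents)**

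| r | u | As written, r(1−u) | Assessed veins only | Upper bound, r(1−u)+u |
|---|---|---|---|---|
| 20% | 10% | 18% | 20% | 28% |
| 20% | 25% | 15% | 20% | 40% |
| 20% | 50% | 10% | 20% | 60% |
| 35% | 10% | 31.5% | 35% | 41.5% |
| 35% | 25% | 26.25% | 35% | 51.25% |
| 35% | 50% | 17.5% | 35% | 67.5% |
| 50% | 10% | 45% | 50% | 55% |
| 50% | 25% | 37.5% | 50% | 62.5% |
| 50% | 50% | 25% | 50% | 75% |

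**The same in counts (also assumed).** Take 30 repeat subjects with 4 isolated veins each, so 120 veins. In 6 of these subjects the veins (24) are not assessed, and 34 reconnections are found.

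- As written: 34/120 = 28.3%.
- Assessed veins only: 34/(120−24) = 34/96 = 35.4%.
- Upper bound: (34+24)/120 = 58/120 = 48.3%.

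**Lead sentence against formula.** The formula takes veins isolated earlier, whether or not they were dealt with at the repeat. The lead sentence speaks of veins targeted at the repeat. On one reading of the lead sentence, a vein checked, found isolated and left alone would drop out of the denominator, which would push the rate up. The two texts do not define one quantity.

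**Whether another rule settles it.** SAP 7.1 bases percentages on subjects without missing data. It concerns subjects, and it does not say that an unassessed vein counts as missing. SAP section 5 keeps subjects treated for non-PV triggers at the index procedure or at blanking-period repeats evaluable for all endpoints, so it does not remove their veins either.

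**The case against.** The strongest reply is that no bias has been shown. The absence of a re-mapping rule does not mean that veins go unmapped. Protocol 14.2.5 separates repeats due to PV triggers from those due to non-PV triggers, and making that distinction would plausibly involve looking at the veins, though the text does not say so. This stands: the effect is conditional, and it is zero if every previously isolated vein is checked.

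A reader might infer that the rate is understated by exactly the share of veins not assessed. That holds against the rate among assessed veins. Against the rate over all previously isolated veins it also needs unassessed veins to reconnect as often as assessed ones (q = r), and nothing in the documents supports that assumption. If the unassessed veins are all still isolated (q = 0), the SAP figure is exactly right and an assessed-only rate would be too high. Operators may also check suspicious veins first, which would make the assessed-only rate selective. This is why the fix asks for bounds as well as a new denominator.

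A reader might also infer that the formula props up a durability claim for this device. Protocol 6.4.3 attributes durable lesions to early reports on other PFA technologies. PV reconnection is a sub-item under repeat ablation among the additional endpoints.

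Finally, the lead sentence and the missing-data convention could be stretched to leave unassessed veins out. Neither does so expressly, and the explicit formula points the other way. The subject-level rate reported alongside does not help: its denominator, the "Total number of subjects undergoing repeat ablation with PVI in all targeted veins at index", also sets no condition on assessment at the repeat.

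**Conclusion.** The point holds as a defect of definition in both SAPs. The vein-level formula treats a previously isolated vein not assessed at the repeat as still isolated. If any such veins exist, it reports r(1−u), the lowest value compatible with the data, against a possible range up to r(1−u)+u. The formula also disagrees with its own lead sentence.

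The size is unknown. The documents give no share of veins unassessed, and the percentages shown rest on assumed values of r and u. They do not support the firmer statement that the rate will be understated by a given amount.

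The practical weight is small. Wave II SAP 7.6 rules out hypotheses and inference for additional endpoints, and Wave I is descriptive throughout. No primary endpoint, error rate or sample size is touched. It is worth correcting because the change is cheap and removes an ambiguity before programming.

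**What to change.** In section 7.6.3 of both SAPs:

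- Restrict numerator and denominator of the vein-level rate to previously isolated PVs assessed for reconnection at a repeat procedure. This follows the principle already used for acute reconnection.
- Reword the lead sentence so that it names the same veins as the formula.
- Report the number of previously isolated veins not assessed. Beside the rate, give the lower bound (all unassessed veins isolated) and the upper bound (all reconnected).
- Confirm that the repeat-procedure form records assessed yes/no for each vein. The form is not among the public documents, so the field may already exist; if not, add it.

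The cost is SAP wording and at most one data field per vein. The denominator will be smaller if any veins are unassessed, the reported rate may be higher, and assessed veins may be a selected group. The bounds disclose that last risk but do not remove it.
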